6 cost, but the problem continues to escalate in many aspects. A recent report indicated
7 that Medicare expenditures were associated with a readmission rate estimated to be \$12
8 billion per year.¹ Another report² has indicated that about 24% of the entire Medicare
9 expenditure is consumed by readmissions. Ironically, those reports were based on data
10 gathered between 1974 to 1977, and definitely would be much higher in today
11 calculations according to current inflation index in GDP. As health care professionals,
12 we should be aware of all ongoing ramifications associated with readmissions, as the
13 integral scope of proper patient care is under scrutiny with all its related issues such as,
14 hospital reimbursement, physician credentialing process and regulation, referral pattern
15 and eventually educational enterprises.³
16

17 **Surgical Site Infections Following Arterial Revascularization with Groin Incision**
18
19

20 Vascular surgery especially arterial revascularizations with groin incisions
21 (ARGI) has always been associated with the potential of higher rates of readmission
22 pertaining to high-risk patients with multiple co-morbidities such as diabetes, cardiac
23 issues and poor general nutrition. These types of issues are more demanding in
24 geographical areas such as rural West Virginia where easy access to medical attention is
25 not available. In most cases, 30 day-readmissions are considered to be in-hospital
26 complications. However, some authorities have suggested that readmissions after
27 vascular interventions are really measures of post discharge complications rather than in-
28 hospital complications.³⁻⁸ Most U.S hospitals are currently in full compliance with the
29 Surgical Care Improvement Project (SCIP). Unfortunately, compliance with these
30 processes has not yet directly been associated with reduced SSI rates.^{9,10} In addition,
31 reports of 30-day readmission rates for vascular surgery patients are very high and it may
32 vary from 11 to 25%.^{1,8}
33

34 Identifying patients with higher rates of readmission after discharge is of essence
35 in order to pay more attention or even to deploy a system to monitor them closely. In one
36 study,¹¹ patients with a positive clinical culture obtained more than 48 hours after hospital
37 admission had an increased hazard of readmission (HR, 1.40; 95% CI, 1.33-1.46) after
38 adjusting for other co-morbidities. Another review indicated that SSIs may develop in

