22 significant resources to achieve its target. As part of the main objectives of telehealth
23 technology, we believe that our suggested approach will limit not only the number but
24 also the frequency of VNS. In addition it may even supersede VNS as it provides to some
25 extent more continuous and more objectives measures to provide a better follow up to our
26 patients after discharge.

27
28 In conclusion, it seems reasonable to believe that monitoring using telehealth
29 technology and managing the general health care patients receive after a hospital vascular
30 ARGI intervention will improve overall health, patient care and will reduce post
31 operative complications. Our project will be conducted to directly give more and
32 continuous attention to postoperative period after hospital discharge. We believe that
33 early readmission is a “failed discharge” as has suggested by others. This matter is of
34 great interest particularly to our specialty.

35 36 37 **Objectives**

38 The primary objective of the current project is to compare outcomes for patients
39 who receive post discharge health care monitoring (which includes using Telehealth
40 electronic monitoring; THEM) to patients who receive standard of care (SOC) and routine
41 discharge instructions and no monitoring.

42 **Outcomes**

43 The primary outcomes include 30-day readmissions, post-operative complications
44 and access site/wound infections. Secondary outcomes will include a pre and post
45 surgery quality of life measures (SF-8) and patient satisfaction (>30-day) along with an
46 occurrence of any 30-day stroke, MI or death.

1
2
3 **Study hypotheses:**
4

- 5 1. A smaller percentage of THEM patients will require a 30-day unplanned
6 readmission.
7 2. A smaller percentage of THEM patients will develop a SSI.
8 3. THEM patients will report greater post discharge satisfaction and higher
9 quality of life measures.

10
11 **Significance:**
12

- 13 1. Information and results obtained from this study may suggest additional post
14 discharge treatment approaches which in turn could lower 30-day
15 readmissions and complications for patients undergoing surgery.
16
17 2. Likewise, information and results obtained from this study could be used to
18 help promote greater patient satisfaction and quality of life measures.
19
20 3. This approach may impact some direct cost pertaining to post-discharge
21 follow-up as visiting nurse services. THEM approach will provide a direct,

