18 following reasons (1) do not plan to do follow-up visit at the VCOE; (2) inability to sign
19 or understand the consent form; (3) do not have home internet service with WIFI or live
20 outside of the provided cell coverage area (cell coverage will be provided for patients
21 without internet WIFI). Informed consent will be obtained research coordinator; eligible
22 patients will be randomly assigned to either the treatment group (THEM) or the control
23 group (SOC).

24
25
26 *Randomization:*

27 The randomization will be done centrally using a computer containing a SPSS algorithm.
28 The randomized list will be placed in 220 envelopes and labeled 1 through 220. After
29 randomization and necessary medical procedures, but before discharge each patient
30 depending on treatment assignment will receive either the home monitoring equipment
31 with instruction for those in the treatment group (THEM) or normal discharge
32 instructions for the control group (SOC).

33
34 Patients in the intervention group will receive a tablet computer and home monitoring
35 medical devices with sensors to transmit the information to a central website that will be
36 monitored by care managers. The TeleMed 2020 electronic home health monitoring
37 system will be used to provide constant surveillance of THEM patients. In addition, the
38 tablets will have the ability to send a high resolution photograph of wound if needed.
39 Medical devices will include weight scales, blood pressure cuffs, thermometers and
40 oxygen saturation monitors.. Clinical care managers will remotely monitor the health of
41 patients by viewing all electronic readings. Study care managers will call or send
42 electronic messages to the patients based on alerts generated by the tele-monitoring
43 system. The main focus of this approach is to have a direct, specific, objective and
44 measurable assessment of any early wound infection after lower extremity
45 revascularization. The care manager will make direct electronic communication as to the

1 appearance of the access wound and if needed request that a picture be sent for
2 observation.

3 4 **TeleMed 2020**

5
6 Bloomberg Business Company Overview of TeleMed 2020, Inc.

7 8 Company Overview

9 TeleMed 2020, Inc. owns and operates a cloud-based SaaS solution for remote patient
10 monitoring. The company allows clinician scheduling and ongoing patient capture and

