11 sharing of critical information yielding earlier and more active care plan management.

12 The company is based in Indianapolis, Indiana.

13
14 <http://www.bloomberg.com/research/stocks/private/snapshot.asp?privcapid=310873357>

15
16
17 For the THEM group, the care manager will:

- 18
19 1. Monitor patient vital signs: daily weight, blood pressure, pulse, , oxygen
20 saturation and temperature
- 21 2. Ask about the description of the postoperative wound site: including any
22 surrounding erythema, discharge, wound dehiscence and healing. If necessary,
23 ask for a picture of the wound site to be sent. A transmitted photograph of the
24 wound condition may augment amount of knowledge available to clinical care
25 management team.
- 26 3. Complete a target organ evaluation: which means to evaluate the bypass and this
27 will include general feeling, pain (location, degree, type and relieving elements).
- 28 4. Assess compliance with the discharge medications.

29
30
31 Early signs of infection would include, but not be limited to fever, tachycardia,
32 discharge, erythema, wound dehiscence, and pain. All of these will be evaluated via
33 telecommunication tools by the care manager and if needed immediately discussed with
34 supervising physician. In addition, the patient, if needed, will be scheduled for an early
35 office visit and/or re-hospitalization.

36
37 For the SOC group, the care manager will follow the current standard of care.

38 39 40 **Procedure:**

41 **PRE-TREATMENT:**

- 42 • Patients will be identified by the Vascular Surgeon and scheduled for the
43 procedure.
- 44 • Study coordinator will review patient scheduling records to identify
45 potential study participants.

- The study coordinator will explain the research study and the informed consent with the patient prior to the surgical intervention.
- The patient upon appropriate consent signs and dates the consent form and the HIPPA authorization form, which is attached to the consent form.
- Patient upon informed consent is randomized to either receive the treatment (THEM) or to the SOC control group (SOC).
- Complete a pre-treatment SF-8 and baseline history form.

Quality of life measure

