The SF-8™ Health Survey is a brief and comprehensive quality of life population survey. It has only eight questionnaire items, and by design according to the company’s website “was constructed to replace the SF-36® and SF-12® in population health surveys in the U.S. and internationally. Accordingly, it has been translated and linguistically validated for use in more than 30 countries and languages using IQOLA Project methods. It has been adopted by federal agencies (e.g., the DOD), leading polling organizations (e.g., the Roper-Starch Worldwide Health Report), and industry sponsors of clinical trials and effectiveness research (e.g., Glaxo Smith Kline, Johnson & Johnson, and Searle).” In addition, the validation and norming measures of the SF-8™ Health included the general population as well as many subgroups of subjects with co-morbidities such as depression and diabetes. The SF-8™ is a very sensitive test that has both test/retest reliability as well as the ability to detect change of time. The scoring of the SF-8™ produces two summary scores. One for the physical (PCS) and one for the mental dimension (MCS). It also provides the same 8 subscale scores for each dimension as the SF-36.

Vascular Intervention:

All patients will receive their planned and scheduled procedures.

Follow-Up Protocol:

After 2-4 weeks, all patients will have a follow-up visit scheduled at the VCOE clinic. Follow-up will include physical exam including a routine visual inspection of access site wound and comments will be collected. All patients will complete a second SF-8 survey form and a patient satisfaction survey. If follow-up visit is less than 30 days, then a member of the study team will call patients and obtain SF-8, satisfaction survey and follow-up form.

Data Collection:

Will include (see appendix):

- 1) Signed consent forms
- 2) Enrollment and demographics form
- 3) SF-8 survey
- 4) Patient satisfaction survey
- 5) 4 week follow-up form

Schedule of Events

Information:	SOC	THEM
Sign Informed Consent	Pre-Intervention	Pre-Intervention
Randomization	Pre-Intervention	Pre-Intervention
Pre-treatment	SF-8 survey	SF-8 survey
Equipment & instructions	At discharge	At discharge
Follow Up:		
Special issue follow-up	Patient initiated	Patient or monitor initiated
Routine follow-up exam	2-4 weeks	2-4 weeks
	SF-8 survey	SF-8 survey
	Satisfaction survey Follow-up form Debriefing	Satisfaction survey Follow-up form Debriefing

1
2
3
4
5
6
7
8
9
10
11
12
13
14
15
16
17
18
19
20
21

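### Allocation precedes surgery but telehealth starts at discharge: counting primary events from discharge and withholding the arm until then would remove dilution and protect the SF-8 baseline at little cost

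*Combined protocol and SAP*

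**What the plan says.** All places are in the combined protocol and SAP.

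- **Allocation.** Procedure, PRE-TREATMENT: consent is obtained before the surgical intervention, and then "Patient upon informed consent is randomized to either receive the treatment (THEM) or to the SOC control group (SOC". The Schedule of Events gives randomisation as pre-intervention in both arms.
- **Start of the intervention.** Under Randomization, the monitoring equipment or the normal discharge instructions are given after "randomization and necessary medical procedures, but before discharge each patient", according to the assigned arm. The Schedule of Events row "Equipment & instructions" says at discharge in both arms.
- **Envelopes.** "The randomized list will be placed in 220 envelopes and labeled 1 through 220". The text does not say that they are sealed or opaque, when they are opened, or who learns the result.
- **Baseline.** "Complete a pre-treatment SF-8 and baseline history form" is the item that follows randomisation in the PRE-TREATMENT list, and the SF-8 row follows the randomisation row in the schedule.
- **Aim.** The Objectives concern patients "who receive post discharge health care monitoring (which includes using Telehealth" electronic monitoring. The Background cites the view that readmissions after "vascular interventions are really measures of post discharge complications rather than in"-hospital ones.
- **Endpoint and analysis.** End Points names 30-day readmissions, post-operative complications and access site or wound infections as primary. Study Design scores unplanned readmission and/or complication as 0/1. No section says when the 30 days begin. Statistical Analysis makes all analyses intention-to-treat, with a per-protocol sub-analysis if possible. The design is open-label with blinded endpoints.

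**The concern.** Telehealth monitoring cannot act before the patient has the equipment. A wound infection or complication during the index stay is expected equally often in both arms, whatever the monitoring later achieves. As written, such an event can still count as a primary event. Equal additions to both arms leave the absolute difference unchanged but raise its variance, so power falls and the relative effect looks smaller.

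The second issue is knowledge of the arm. If the envelope is opened at consent in an open-label trial, the patient may complete the self-reported baseline SF-8 knowing the arm, and ward staff may know it when discharge is decided. Blinded endpoint assessment protects the classification of events. It does not protect a self-reported baseline or the discharge decision.

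**Working it through.** **1. Sequence.** Set side by side, the Procedure list, the Randomization text and the Schedule of Events agree: consent and allocation, then surgery, then equipment at discharge. The stay between allocation and discharge lies inside the trial but outside the intervention.

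**2. Which primary components are exposed.** A readmission requires a prior discharge, so it cannot occur in that interval. Wound infection and post-operative complication can. Sample Size states its rates for infection/readmission, so within the powered endpoint only in-hospital wound infection is exposed.

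**3. The plan's own figure.** Inputs from Sample Size: 12% versus 2%, two-sided 0.05, 200 evaluable (100 per arm), 220 enrolled (110 per arm). Pooled normal approximation at n = 100:

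Power = Φ{[|p1−p2|√n − 1.96√(2p̄(1−p̄))] / √(p1(1−p1)+p2(1−p2))}, with p̄ = 0.07

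= Φ{[1.000 − 1.96×0.3608] / 0.3538} = Φ(0.827) = 79.6%.

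This reproduces the stated 80%. At 110 per arm it gives 83.3%. Exact enumeration over both binomials with the uncorrected chi-square test gives 83.7% at 100 and 87.6% at 110. Fisher's test, which the plan also allows, gives 76.2% and 81.3%.

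**4. Adding in-hospital infection.** The documents give no in-hospital rate, so d is an assumption. Add d to each arm and repeat the exact chi-square calculation:

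| d (points) | Rates | 100 per arm | 110 per arm |
|---|---|---|---|
| 0 | 12% vs 2% | 83.7% | 87.6% |
| 1 | 13% vs 3% | 78.1% | 82.4% |
| 2 | 14% vs 4% | 73.0% | 77.4% |

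Power reaches 80% at about 0.65 added points with 100 per arm and about 1.5 with 110. If 12% and 2% already include in-hospital infection, d is zero and there is no added loss.

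**5. What moving randomisation to discharge would add.** Counting from discharge deals with step 4 wherever randomisation sits. Moving randomisation adds only the exclusion of patients never discharged home. Suppose a share t of THEM patients is unexposed and keeps the 12% rate, so p2 = 2% + 10%×t. If a share f is never discharged home and so not randomised, the unexposed share becomes (t−f)/(1−f).

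- t = 5%: p2 = 2.5%, power 77.6% (82.0% at 110). With f = 2.5%: 0.025/0.975 = 2.56%, p2 = 2.256%, power 80.6% (84.9%).
- t = 10%: p2 = 3.0%, power 70.9% (75.7%). With f = 5%: 0.05/0.95 = 5.26%, p2 = 2.526%, power 77.2% (81.7%).
- f = 0: no gain.

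Both t and f are assumed. The model is also generous, because a patient who never leaves hospital cannot be readmitted and is unlikely to carry a 12% rate in either arm.

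**The case against.** **The design is legitimate.** Allocation before surgery with intention-to-treat analysis gives a valid comparison and fixes the cohort before the post-operative course is known. This stands. A reader might infer that early allocation biases the trial or that the sections conflict on timing. Neither is supported: the comparison remains randomised, and the sections agree.

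**Randomisation need not move.** A reader might infer that the envelope must be opened at discharge clearance and randomisation shifted with it. The documents do not support that as a requirement. Removing in-hospital events comes from the counting window, and a clean baseline comes from the order of tasks. The gain unique to moving randomisation is unknown and may be zero. It would bring scope for selective enrolment once the post-operative course is known, more consents than randomisations (220/0.95 = 231.6, so 232, if an assumed 5% are lost; 220/0.90 = 244.4, so 245, if 10%), and a population narrower than any planned groin cut-down. This stands in full.

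**The loss may be small.** At 110 per arm, chi-square power stays at about 80% or better up to about 1.5 added points. This stands, though less comfortably under Fisher's test, which starts at 81.3%. A much larger loss could be produced by adding a broad complication rate to 12% and 2%, but those rates are stated for infection/readmission, and no complication rate is given to add.

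**Influence on the SF-8 or on discharge is conjecture.** List order need not be time order, the SF-8 is secondary, and nothing shows that such influence occurs. This stands, but nothing in the text prevents it.

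**A per-protocol sub-analysis is planned.** It bears on patients who never receive equipment. It can break the randomised comparison, and it does not of itself exclude in-hospital events.

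**Conclusion.** The point holds as a cheap improvement, not as an error. Followed as written, the plan can count infections and complications that arise before telehealth begins, and it leaves open that the arm is known at the baseline SF-8 and during the hospital stay.

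The effect on power depends on a rate that the documents do not give. If in-hospital infection comes on top of the planning rates, each of the first two added points costs about 5 percentage points of exact chi-square power at either sample size. If the planning rates already include it, the added cost is nil. The dilution from in-hospital complications in the wider 0/1 endpoint cannot be sized from the documents. The exposure of the SF-8 baseline and the discharge decision is a possibility left open, not a demonstrated bias.

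**What to change.** 1. Complete the baseline SF-8 and history form before allocation, and reorder the PRE-TREATMENT list and the schedule accordingly.
2. State that the numbered envelopes are sealed, opaque and used in sequence, and that the arm stays undisclosed to patient and staff until the patient is cleared for discharge.
3. Count primary readmission, complication and wound-infection events for 30 days from discharge in both arms.
4. Record events already present at discharge separately as baseline, and report in-hospital events by arm.
5. Report patients never discharged, by arm.

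Items 2 and 3 belong together. Starting the clock at discharge is safe when discharge cannot depend on the arm, which is what withholding the arm secures.

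**Cost.** Mostly wording. In-hospital events leave the primary endpoint, and patients never discharged do not contribute to it, hence the separate reporting. Someone must open or disclose the allocation at all 220 discharges, whereas now only about 110 THEM discharges need study equipment; the plan has one half-time nurse as coordinator and care manager. The telephone contact already planned for patients seen before 30 days can collect the outcome, provided it is timed from discharge.

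**Option.** The sponsor may also move randomisation itself to discharge clearance. If so, every consented but unrandomised patient should be logged and reported with the reason. That makes selective enrolment visible but does not prevent it.

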22 measurable, specific tool to provide therapy related information to the treating
23 physician during post-discharge period.
24

25
26 **Study Design:**
27

28 The current study is designed to be a **prospective, randomized, open-label, single-**
29 **center with blinded endpoints (PROBE) study.**¹⁴ More specifically, it is designed to test
30 the hypothesis that Tele-health monitoring will decrease 30-day readmission and
31 complication rates. Patients with planned vascular ARGIs will be consented for possible
32 inclusion. Patients who give their consent will be enrolled and randomly assigned to one
33 of the two treatment arms: 1) standard of care (SOC) or 2) Tele-health electronic
34 monitoring (THEM) using TeleMed 2020 home health monitoring system.
35 The primary endpoints will be measured as simply the occurrence or not of any
36 unplanned 30-day readmission and/or complication (0/1). Patients in the intervention
37 group (THEM) will receive a tablet computer and home monitoring medical devices with
38 sensors to transmit the information to a central website that will be monitored by care
39 managers. Medical devices will include weight scales, blood pressure cuffs and oxygen
40 saturation monitors. Clinical care managers will remotely monitor the patients and all
41 electronic readings. Clinical care managers will call or send electronic messages to the
42 patients based on alerts generated by the tele-health monitoring system.
43

44 **Sample:**

1
2 The population for this study will be patients with any planned vascular procedures with
3 cut-down access to the groin and will be treated by one of the Vascular Surgeons in the
4 Vascular Center of Excellence (VCOE).

5
6 *Sample Size:*

7 The sample size was estimated based on the readmission rates from a previous research
8 study. An overall sample size of 200 subjects will have 80% power to detect a reduction
9 in the 30-day infection/readmission rate from ~12 in the SOC group to ~2% in the THEM
10 group using a 2-sided α of 0.05. We expect a 10% drop-out rate and thus plan to enroll
11 110 patients in each group (N=220 overall).

12
13
14 *Inclusion/exclusion criteria:*

15 Patients meeting the inclusion criteria, which is any planned vascular procedures with
16 cut-down access to the groin and treated by one of the Vascular Surgeons in the Vascular
17 Center (VCOE) will be consented and enrolled. Patients will be excluded for any of the

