22
23
24
25
26
27
28
29
30
31

SOC = Standard of Care
THEM = Tele-Health Electronic Monitoring

Statistical Analysis:

All analyses will be based on intention-to-treat (ITT) analyses. However, if possible we will sub-analyze the data on a per-protocol basis as well. Descriptive statistics will be expressed in terms of frequencies, percentages, or means \pm standard deviation (SD). Categorical variables will be tested by chi-square or Fisher exact tests and continuous variables will be tested by student t-test or paired t-test for pre/post measures, where deemed appropriate. Survival and freedom from event curves such as freedom from re-admission will be created using the Kaplan Meier method, compared by the Log Rank test, and graphically presented using life tables. All probability values will be 2 sided and ‘p’ values <0.05 will be considered significant. Statistical analyses will be performed using SPSS version 19.0 for Windows. This study will be registered at ClinicalTrials.gov.

End Points:

The primary outcomes include 30-day readmissions, post-operative complications and access site/wound infections.

Secondary outcomes will include a pre and post-surgery quality of life measures (SF-8), patient satisfaction (>30-day) and number of VNS visits along with an occurrence of any 30-day stroke, MI or death.

Definitions:

1
2 Event-free survival will be defined as the freedom from unplanned 30-day
3 readmission and/or 30-day access site wound infection.

4
5 **Human Subjects**

6 **Recruitment Method(s)**

7
8 The current study protocol received approval from our local institutional review
9 board. The study group participants will sign consent papers on admission to the
10 vascular lab when the patient presents for pre-procedure evaluation. The study care
11 manger will identify potential study participants, and provide information about the
12 study. Study staff will be trained and knowledgeable on the research protocol. This
13 study will not offer any direct benefit for the study participants. Staff will not begin
14 consenting patients until they have completed this training and are in compliance with
15 any pertinent trainings offered by Research and Grants.

16
17 **Payment/Costs of Testing:**

18
19 Patients enrolled in both study comparison groups (THEM and SOC) will not
20 incur additional expenses as a due to their participation in this study. Normal standard of

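### No test for ordered outcomes is planned: if satisfaction answers are analysed as ordered categories, chi-square ignores their order and loses power on the satisfaction part of hypothesis 3

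*Combined protocol and SAP*

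**What the plan says.** - **Tests.** Statistical Analysis gives one rule for all outcomes that are not event curves: "Categorical variables will be tested by chi-square or Fisher exact tests and continuous variables will be tested by student t-test", continuing "or paired t-test for pre/post measures, where deemed appropriate". Log-rank is reserved for freedom-from-event curves. On significance testing it says "All probability values will be 2 sided", with a 0.05 threshold.
- **Hypothesis.** Study hypotheses, item 3, is directional: "THEM patients will report greater post discharge satisfaction and higher" quality of life. Satisfaction is listed as a secondary outcome under Outcomes and again under End Points.
- **Collection.** Follow-Up Protocol says "All patients will complete a second SF-8 survey form and a patient satisfaction survey". The Schedule of Events shows the satisfaction survey in both arms at follow-up only, so there is no baseline value.
- **Scoring.** For the SF-8, the quality-of-life section says "The scoring of the SF-8™ produces two summary scores", one physical and one mental. For the satisfaction survey, the supplied text gives no number of items, response format or scoring. Data Collection refers to an appendix that was not supplied.
- **Power.** Sample Size states "An overall sample size of 200 subjects will have 80% power to detect a reduction" "in the 30-day infection/readmission rate from ~12 in the SOC group to ~2% in the THEM" group. No effect size or power is stated for satisfaction.

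**The concern.** Because satisfaction is measured once, the paired t-test cannot apply, and the comparison has to be between arms. The between-arm tests on offer are chi-square or Fisher for categories and Student's t-test for continuous values. Satisfaction questions are often answered on a short ordered scale. If this one is, and its answers are treated as categories, the rule leads to chi-square or Fisher. Two things follow.

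1. **The test does not match the claim.** On three or more levels, Pearson chi-square gives the same result however the columns are ordered. It can be significant when monitored patients use both extremes more often and are no more satisfied overall. A significant result would then not by itself show the greater satisfaction that the hypothesis states.
2. **Power is spread thin.** With *k* levels the evidence is shared over *k* − 1 degrees of freedom, while a rank test puts it all on one.

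The trial is also open-label, and the test for this outcome is not named. Naming it beforehand removes a choice that could otherwise be made after the data are seen.

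**Working it through.** **1. The plan's own power figure.** Inputs from Sample Size: 12% against 2%, two-sided 0.05, 100 per arm. The mean rate is 0.07.

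- n per arm = [1.960·√(2·0.07·0.93) + 0.842·√(0.12·0.88 + 0.02·0.98)]² / 0.10² = (0.707 + 0.298)² / 0.01 ≈ 101.0, rounded up to 102. That is 204 in total, against 200 stated.
- Power at 100 per arm: z = (√100·0.10 − 0.707) / 0.354 = 0.83, which gives 79.6%.

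The figure reproduces. It concerns infection/readmission only and says nothing about satisfaction.

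**2. Analytic check of the degrees-of-freedom cost.** A one-degree-of-freedom test with 80% power at two-sided 0.05 has noncentrality (1.960 + 0.842)² = 7.85. Giving the same noncentrality to a chi-square with *k* − 1 degrees of freedom yields:

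| Levels *k* | 5% critical value | Power |
|---|---|---|
| 2 | 3.84 | 80% |
| 3 | 5.99 | 71% |
| 4 | 7.81 | 64% |
| 5 | 9.49 | 60% |
| 7 | 12.59 | 52% |
| 10 | 16.92 | 45% |

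**3. Simulation.** The documents give no response scale, control distribution or effect for satisfaction, so all three are assumed. Each scenario has 20,000 trials, 100 per arm, two-sided 0.05. The monitored arm is shifted by a common odds ratio: each cumulative control probability *c* becomes *d*, with *d*/(1 − *d*) = [*c*/(1 − *c*)] / OR. For example, controls at 5, 10, 20, 35, 30% (worst to best) with OR 2.0 give 2.6, 5.5, 13.1, 32.6, 46.2% under monitoring.

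Power at OR 2.0:

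| Control distribution, worst to best (%) | Chi-square | Wilcoxon | t-test on scores | Loss, chi-square vs Wilcoxon (points) |
|---|---|---|---|---|
| 2 levels: 40, 60 | 63% | 62% | 62% | about 0 |
| 3 levels: 20, 30, 50 | 60% | 71% | 69% | 11 |
| 4 levels: 10, 20, 30, 40 | 57% | 74% | 72% | 17 |
| 5 levels: 20 each | 57% | 78% | 78% | 21 |
| 5 levels: 5, 10, 20, 35, 30 | 54% | 76% | 73% | 22 |
| 5 levels: 10, 15, 25, 30, 20 | 56% | 78% | 77% | 22 |
| 5 levels: 2, 3, 10, 25, 60 (ceiling) | 41% | 64% | 57% | 23 |
| 7 levels: 5, 5, 10, 20, 25, 20, 15 | 49% | 79% | 76% | 29 |
| 10 levels: 10 each | 43% | 80% | 80% | 37 |

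Repeat runs moved these by a point or so. A further five-level distribution (3, 5, 12, 30, 50%) gave chi-square 45 to 47% and Wilcoxon 70%, a loss of up to 25 points. So the ranges to carry forward are about 10 points for three levels, 16 to 17 for four and 21 to 25 for five.

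**4. Sensitivity to the effect.** For five levels, the loss over odds ratios 1.25 to 3.0 runs from about 4 to 23 points in the scenarios tabulated above. It is small at both ends, where both tests have little power or both have a lot. With no true difference, all three tests reject in about 4 to 5% of trials, so this is a question of power and not of false positives.

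**5. The t-test branch.** In most scenarios the t-test on item scores is within about 3 points of Wilcoxon. With half or more of the controls in the top category it falls up to about 7 points below.

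**The case against.** The strongest reply is that the plan never assigns satisfaction to chi-square. It offers a categorical and a continuous branch, qualified by "or paired t-test for pre/post measures, where deemed appropriate", and the second branch recovers nearly all the power if answers are scored or summed. The scale is unknown, and with a yes/no item nothing is lost. Every simulated effect is a proportional-odds shift, the pattern that suits Wilcoxon. Frequencies and percentages will be reported, so a reader would see a shift towards both extremes. The outcome is secondary and has no stated power.

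Most of this stands, and it limits the point. It rules out three stronger readings that a reader might infer:

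- **That the trial loses about 20 points of power.** That size belongs to a five-level item tested by chi-square at an odds ratio near 2. Over the scenarios examined, the loss runs from 0 to 37 points, and the documents do not say which applies.
- **That hypothesis 3 as a whole is weakened.** Its quality-of-life half rests on SF-8 summary scores, which fall under the t-test. No loss is shown there.
- **That a real gain in satisfaction is likely to be missed.** No expected gain is stated. At an odds ratio of 2.0, five-level chi-square power is roughly even; at 2.25, under three assumed control distributions, it is 61 to 71%.

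What the reply does not remove is that no listed test uses the order of categorical answers. The phrase about appropriateness leaves the analyst choosing among the listed tests and does not add an ordinal one. Descriptive percentages show direction but do not test it.

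**Conclusion.** The point holds in conditional form. If satisfaction answers have three or more ordered levels and are analysed by category, the stated rule gives a test that ignores the ordering and does not by itself address greater satisfaction. The power figures assume 100 evaluable patients per arm, a proportional-odds shift with odds ratio 2.0, and the control distributions shown. If answers are scored and compared by t-test, what remains is usually within about 3 points of Wilcoxon, or up to about 7 with a ceiling. The mismatch between test and claim needs no assumed effect size, but it does need the ordered-category assumption. SF-8 scores, the primary endpoint and the sample size are untouched. This is a free improvement to a secondary outcome, not a flaw that threatens the trial.

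**What to change.** In Statistical Analysis, say how satisfaction is scored, and add that satisfaction items with three or more ordered answers are compared between arms by the Wilcoxon rank-sum test, or by a proportional-odds model reporting the common odds ratio. Keep chi-square or Fisher for binary and unordered variables, and the t-test for many-valued totals.

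The cost is a sentence or two of wording, settled before the data are examined. Both methods are standard in SPSS, which the plan already uses. No extra data, visits or patients are needed. If the survey turns out to yield only a many-valued total, the gain over the t-test is small and the sentence does no harm.
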